##### **6.4.1.1. 24-Hour Urine Collection**

Patients will be required to provide two separate valid 24-hour urine collections 2 weeks prior to randomization (to assess eligibility after the run-in period), at Week 32 (to assess the primary endpoint), and at the EOS/ET visit. Patients will also be asked to provide a single valid 24-hour urine sample for other 24-hour urinary assessments outlined in the Schedule of Assessments ([Table 1](#), [Table 2](#), [Table 3](#), and [Table 4](#)). Both UPCR as well as UACR will be calculated in an aliquot of each 24-hour urine collection. Rigorous exercise and significant change in diet (in particular salt intake) should be avoided within 48 hours before collection of 24-hour urine samples, whenever possible. The two valid 24-hour urine samples may be collected within 2 weeks before assessment is due while the one valid 24-hour urine sample may be collected within one week before the assessment takes place. If any of the collections do not meet validity criteria outlined below, then repeat collections must be scheduled within the time frames outlined above to assure the minimum number of valid collections required for each of the study time points. The duration of collection and volume of urine in the collection will be recorded in the eCRF. In addition to protein, albumin, sodium and creatinine will also be quantified in each of the 24-hour urine samples.

A 24-hour urine collection will only be considered valid if the following criteria are met, otherwise a repeat urine collection will be required:

- The collection is between 22-26 hours in duration between the initial discarded void and the last void or attempt to void.
- No voids are missed between the start and end time of the collection as indicated by the patient's urine collection diary.

Primary efficacy will be evaluated by comparing the percent change from baseline in 24-hour UPCR at Week 32 in patients treated with cemdisiran versus those treated with placebo.

Secondary and exploratory efficacy assessments include comparisons of the proportion of patients with partial or complete clinical remission, respectively, as measured by the amount of total protein in a 24-hour urine sample. Partial clinical remission is defined as having UP <1 g/24-hours and complete clinical remission is defined as UP <0.3 g/24-hours. Each will be assessed at Week 32.

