### 7.1. Determination of Sample Size

The sample size of the study was determined based on the precision of the estimate of the treatment effect for the primary endpoint – the percent change from baseline in UPCR from a 24-hour urine sample at Week 32. It should be noted that geometric mean ratio of UPCR at Week 32 to baseline is statistically equivalent to mean of the change from baseline in logarithm of UPCR. Therefore, the effect size of the study is defined as the difference of change from baseline between cemdisiran and placebo in the logarithm of UPCR.

Based on the [\[Fellstrom 2017\]](#) study, we assume that in the placebo arm the geometric mean ratio of UPCR at Week 32 to baseline is 0.88 (log standard deviation [SD] 0.597), corresponding to a 12% reduction, while the geometric mean ratio is 0.5, or a 50% reduction for the cemdisiran arm. Using these assumptions, sample size of 9 and 18 in the placebo and cemdisiran arms will provide a width of 0.80 ( $\pm 0.4$ ) for the 90% confidence interval (CI) for treatment effect size estimate (cemdisiran – placebo) in log scale.

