## 7.2.5. Efficacy Analyses

### 7.2.5.1. Primary Endpoint

The primary endpoint of the study is the percentage change from baseline in 24-hour UPCR at Week 32. The 24-hour UPCR will be log transformed for analyses. The primary analysis will be performed using a restricted maximum likelihood (REML) based Mixed-Effect Model Repeated Measures (MMRM) approach. The outcome variable is change from baseline in 24-hour UPCR in log-scale at the Week 16 and Week 32 visits. Analysis will include fixed effects of treatment (cemdisiran vs. placebo), scheduled visits (Week 16 and Week 32), interaction term of treatment and scheduled visits, baseline 24-hour UPCR in log-scale (continuous), and patient as a random effect. The least square mean difference and its 90% confidence interval will be estimated. In addition, placebo-adjusted geometric mean percent change at the Week 32 visit and its 90% CI will be presented.

A sensitivity analysis for the impact of missing data and the normality assumptions on the log-transformed UPCR data will be performed. Details will be provided in the SAP.

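### The primary MMRM states only a random patient effect within patients, which read literally gives Week 16 (one urine collection) and Week 32 (two) the same variance; a visit-specific covariance should be written instead

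*Protocol*

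**What the plan says.** Section 7.2.5.1 names a "restricted maximum likelihood (REML) based Mixed-Effect Model Repeated Measures (MMRM) approach" for the log change from baseline in 24-hour UPCR at Weeks 16 and 32. The terms are treatment, visit, treatment by visit, "baseline 24-hour UPCR in log-scale (continuous), and patient as a random effect". No residual covariance structure is given. The result to be reported is an interval: "The least square mean difference and its 90% confidence interval will be estimated".

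The visits are not measured alike. Section 6.4.1.1 requires two valid 24-hour collections "after the run-in period), at Week 32 (to assess the primary endpoint), and at the EOS/ET visit". For the remaining visits, which include Week 16, "Patients will also be asked to provide a single valid 24-hour urine sample for other 24-hour urinary assessments". Section 7.2.4 says that the two pre-randomization collections are averaged to form the baseline. Section 7.2 has no matching sentence for the two Week 32 collections.

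Section 7.1 sizes the trial on precision. It assumes a placebo "geometric mean ratio of UPCR at Week 32 to baseline is 0.88 (log standard deviation [SD] 0.597", and for active treatment, "while the geometric mean ratio is 0.5, or a 50% reduction for the cemdisiran arm". It concludes that a "sample size of 9 and 18 in the placebo and cemdisiran arms will provide a width of 0.80" for the 90% CI.

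**The concern.** A random patient effect plus an ordinary residual has two variance parameters and implies the same variance at each visit. This design gives a reason to expect unequal variances, because averaging two collections removes half of the collection error at Week 32 and none of it at Week 16. Response spread may also differ between 16 and 32 weeks of treatment. When the variances differ, the pooled variance gives a Week 32 standard error that belongs to neither visit.

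No hypothesis test is attached to the primary endpoint. The trial was sized on the width of the Week 32 interval and will be read from that interval, so its calibration matters. Section 7.2.5.2 carries the same approach over to 24-hour urine protein.

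**Working it through.** **Inputs from section 7.1:** log SD of change 0.597, taken as the Week 32 SD; 9 placebo and 18 cemdisiran patients; 90% two-sided interval, z = 1.645. **Not in the protocol, so assumed:** the collection-to-collection log SD of 24-hour UPCR (s, range 0.10 to 0.50) and the Week 16 log SD.

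**1. The plan's own figure.** sqrt(1/9 + 1/18) = 0.4082. Half-width = 1.645 × 0.597 × 0.4082 = 0.401, width 0.802. The stated 0.80 reproduces. With a t quantile on 25 df the half-width is 0.416.

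**2. Effect of a common variance.** With complete data, and apart from chance baseline imbalance:
- separate Week 32 variance: SE = sqrt(v32 × (1/9 + 1/18))
- random patient intercept: SE = sqrt(((v16 + v32)/2) × (1/9 + 1/18))

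The ratio of the second to the first is r = sqrt((v16 + v32)/(2 × v32)). True coverage of the nominal 90% interval is about 2Φ(1.645 r) − 1.

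**3. Only the number of collections differs.** Collection error contributes s² at Week 16 and s²/2 at Week 32, so v16 = v32 + s²/2, with v32 = 0.597² = 0.356.

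| s (assumed) | r | half-width | coverage |
|---|---|---|---|
| 0.10 | 1.004 | 0.402 | 90.1% |
| 0.20 | 1.014 | 0.406 | 90.5% |
| 0.30 | 1.031 | 0.413 | 91.0% |
| 0.40 | 1.055 | 0.423 | 91.7% |
| 0.50 | 1.084 | 0.435 | 92.5% |

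The interval is mildly conservative throughout. Simulation (4,000 trials per setting, within-patient correlation 0.6) agrees: for s = 0.15, 0.30 and 0.40 the random-intercept model covered 90.2%, 91.1% and 91.4%, with no material bias. With 10% of Week 32 values missing at random and s = 0.30 it covered 90.5%, again without material bias.

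**4. Week 16 less variable than Week 32.**

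| Week 16 log SD (assumed) | r | half-width | coverage |
|---|---|---|---|
| 0.45 | 0.885 | 0.355 | 85.5% |
| 0.40 | 0.851 | 0.341 | 83.8% |

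The interval is 11% to 15% too narrow. Simulated coverage at these SDs ran from about 84% to 87%, depending on the degrees of freedom used.

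**5. On the percent scale.** The assumed effect is ln(0.5/0.88) = −0.565. A half-width of 0.401 gives a placebo-adjusted reduction of 15% to 62%. A half-width of 0.423 (s = 0.40) gives 13% to 63%. A half-width of 0.341 (Week 16 SD 0.40) gives 20% to 60%.

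**6. Can steps 3 and 4 hold together?** With a two-collection baseline, collection error alone gives the Week 16 change an SD of sqrt(s² + s²/2). For s = 0.40 that is 0.49, already above 0.45. For s = 0.30 it is 0.37, which leaves 0.40² − 0.135 = 0.025 or 0.45² − 0.135 = 0.068 for real response variance. So the narrow-interval case needs fairly small collection error.

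**The case against.** The strongest reply is that the protocol never restricts the model to a random intercept. It calls the analysis an MMRM, a label that commonly means a within-patient covariance modelled by visit. Section 7.2 describes itself as a summary and leaves fuller plans to the SAP, which was not available here. A random patient effect with a separate residual variance at each visit would be adequate, and nothing written forbids it. On that view the covariance structure is simply unstated, which is ordinary at protocol stage.

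Part of this stands. That the random intercept is the whole structure is a literal reading, not an explicit statement. But a within-patient term is stated, and section 7 says that the SAP implements the protocol's principal features. Nor can the usual unstructured MMRM be added on top: with two visits it already uses three parameters, and a further patient variance cannot be identified. Replacing the term is therefore a change to the text, not an elaboration of it.

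A reader might infer that the Week 32 interval is wrong, or that it will under-cover. The documents do not support that. The one feature they establish, one collection against two, makes the interval slightly too wide. Under-coverage needs spread to grow between Weeks 16 and 32, and no section gives a Week 16 SD or says that it does. The averaging of the two Week 32 collections is likewise implied, not written.

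**Conclusion.** The concern holds in a limited form. As written, the model ties the Week 32 interval to an equal-variance assumption that the collection schedule gives reason to doubt. For the mechanism that the protocol does establish, the cost is small: about 3% to 5.5% extra width if the collection log SD is 0.3 to 0.4, and no material bias in the estimate. The loss of coverage in step 4 of the working depends wholly on an assumed smaller Week 16 variance; the written model would not guard against it. All sizes rest on the 9-versus-18 evaluable sample, complete data unless noted, and 0.597 as the Week 32 SD. Severity is minor to moderate.

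**What to change.** In section 7.2.5.1, replace the random patient effect with an unstructured 2x2 within-patient covariance for Weeks 16 and 32, and name Kenward-Roger degrees of freedom. Use the same model for 24-hour urine protein in section 7.2.5.2. State that the two Week 32 collections are averaged in the same way as at baseline. A baseline-by-visit term is optional, since no gain from it has been shown here.

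The cost is a line or two of text and one extra covariance parameter (three instead of two). Where the two variances are in fact equal, estimating the Week 32 variance separately costs about 1% in width: the mean simulated half-width was 0.420 for a Week 32-only analysis against 0.415 for the random intercept. The planned half-width of 0.401 in section 7.1 already uses the Week 32 SD alone, so the sample size justification does not change.

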### 7.2.5.2. Secondary Efficacy Endpoints

The secondary efficacy endpoints include percent change from baseline in 24-hour proteinuria (g/24 hours) at Week 32, percent of patients with partial clinical remission (UP <1.0 g/24-hours), percent of patients with >50% reduction in 24-hour proteinuria, change from baseline in UPCR as measured in a spot urine at Week 32 and change from baseline in hematuria at Week 32.

The percentage of patients with partial clinical remission or with >50% reduction in 24-hour proteinuria for each treatment arm and the difference between treatment arms will be presented together with an approximate 90% confidence interval based on Wilson score method.

Change from baseline in UP in 24-hour urine assessments and UPCR by spot urine at Week 32 will be analyzed similarly to the analysis of the primary variable as appropriate. The descriptive statistics for change from baseline in hematuria (urine dipstick) at Week 32 will be provided.

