## 2. OBJECTIVES AND ENDPOINTS

Objectives	Endpoints
Primary	

To evaluate the effect of cemdisiran on proteinuria in adult patients with immunoglobulin A nephropathy (IgAN)

Secondary	

Percent change from baseline in UPCR as measured in 24-hour urine at Week 32

To evaluate the effect of cemdisiran on additional measures of proteinuria in adult patients with IgAN

To evaluate the effect of cemdisiran on hematuria in adult patients with IgAN

To evaluate the safety and tolerability of cemdisiran

Percent change from baseline in 24-hour proteinuria (g/24-hours) at Week 32

Percent of patients with partial clinical remission (urine protein [UP] <1.0 g/24-hours) at Week 32

Percent of patients with >50% reduction in 24-hour proteinuria at Week 32

Change from baseline in UPCR as measured in a spot urine at Week 32

Change from baseline in hematuria at Week 32

Frequency of AEs

Exploratory	

To evaluate the effect of cemdisiran on renal function parameters

To evaluate the effect of cemdisiran on full clinical remission and measures of albuminuria in adult patients with IgAN

To evaluate the pharmacodynamic (PD) effect of cemdisiran ie, C5 level and CAP/CCP

To characterize the pharmacokinetics (PK) of cemdisiran and relevant metabolites in plasma and urine in adult patients with IgAN

To evaluate the effect of cemdisiran on serum and urine markers of complement activation, renal damage and inflammation

Change from baseline in estimated glomerular filtration rate (eGFR) at Week 32

The slope of eGFR computed for the first 36 weeks using all assessments during the period

The slope of eGFR computed for the entire study period, including the open label extension, using all assessments during the study.

Change from baseline in creatinine clearance at Week 32

Percent of patients in full clinical remission (UP <0.3 g/24-hours) at Week 32

Change from baseline in 24-hour albuminuria at Week 32

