### **Patient and Disease Characteristics**

2. Clinical diagnosis of primary IgAN as demonstrated by historical biopsy collected within 60 months of screening
3. Treated for IgAN with stable, optimal pharmacological therapy. In general, stable and optimal treatment will include maximum allowed or tolerated ACE inhibitor or an ARB for at least 3 months prior to start of run-in period.
4. Urine protein  $\geq 1$  g/24-hour at Screening from a valid 24-hour urine collection (see Section 6.4.1.1), and mean urine UP  $\geq 1$  g/24-hour from two valid 24-hour urine collections at the end of the run-in period, prior to randomization
5. Hematuria as defined by  $\geq 10$  RBCs per high powered field (RBC/hpf) by microscopy or a positive urine dipstick (2+ [moderate] and above) measured by a central laboratory at screening

6. Females of child-bearing potential must have a negative pregnancy test, cannot be breast feeding, and must be willing to use a highly effective method of contraception 14 days before first dose, throughout study participation, and for 90 days after last dose administration
7. Previously vaccinated with meningococcal group ACWY conjugate vaccine and meningococcal group B vaccine or willingness to receive these vaccinations as well as prophylactic antibiotic treatment, if required by local standard of care
8. Previously vaccinated or willingness to receive vaccinations for Hib and *Streptococcus pneumoniae* according to current national/local vaccination guidelines for vaccination use

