### **6.1.2. Retesting**

If in the Investigator's judgement, the laboratory abnormalities at screening or in the run-in period are likely to be transient, then laboratory tests may be repeated. The Investigator's rationale is to be documented. Laboratory values can be retested once during screening or the run-in period as long as the patient can be evaluated for eligibility and randomized within the allowed Screening or run-in period. Two retests will be permitted for hematuria during Screening, if the first test is negative.

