#### **6.4.2. Hematuria**

Hematuria from spot urine collections will also be evaluated to assess the effect of cemdisiran on disease course in patients with IgAN. The degree of hematuria will be assessed by microscopic examination of the spun urine sediment (RBC/hpf) and by urine dipstick. Single void collections for random urine sample for hematuria evaluation should be collected. If the investigator determines that the hematuria is transient due to menses in women or exercise, the sample may need to be repeated.

Random spot urine samples for hematuria measurement will be collected throughout the study as outlined in the Schedule of Assessments ([Table 1](#), [Table 2](#), [Table 3](#), and [Table 4](#)) and will be analyzed by a central laboratory. On dosing days, samples should be collected prior to study drug administration, if applicable.

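### Hematuria is the only secondary efficacy endpoint in Section 7.2.5.2 without a between-arm estimate, and no baseline is named for it as an efficacy endpoint

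*Protocol*

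**What the plan says.** The secondary objective in Section 2 is "To evaluate the effect of cemdisiran on hematuria in adult patients with IgAN", and the endpoint is change from baseline at Week 32. Section 7.2.5.2 lists five secondary efficacy endpoints and treats them as follows.

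- Partial clinical remission and more than 50% reduction in 24-hour proteinuria: "the difference between treatment arms will be presented together with an approximate 90% confidence interval based on Wilson score method".
- 24-hour urine protein and spot UPCR: "will be analyzed similarly to the analysis of the primary variable as appropriate". For the primary variable, Section 7.2.5.1 states: "The least square mean difference and its 90% confidence interval will be estimated".
- Hematuria: "The descriptive statistics for change from baseline in hematuria (urine dipstick) at Week 32 will be provided".

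Adverse event frequency is also a secondary endpoint, but it is a safety endpoint and is handled elsewhere.

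Three further provisions bear on how a change in hematuria would read. Inclusion criterion 5 admits a patient on at least 10 RBC/hpf by microscopy or on "a positive urine dipstick (2+ [moderate] and above) measured by a central laboratory at screening". Section 6.1.2 adds: "Two retests will be permitted for hematuria during Screening, if the first test is negative". Section 6.4.2 says of hematuria samples: "If the investigator determines that the hematuria is transient due to menses in women or exercise, the sample may need to be repeated".

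**The concern.** An objective about the effect of a drug needs a comparison with placebo. The protocol randomizes 2:1 and uses the placebo arm to estimate a difference for every other secondary efficacy endpoint, but for hematuria it specifies only a description of change. A reader of the results would have to compare the arms by eye, with no measure of uncertainty, in a study of about 30 patients.

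A description of change also leans on the baseline more heavily than a contrast does, and none is named for this endpoint. Patients are selected for hematuria at Screening on up to three tests, so change measured from the qualifying test would tend to look like improvement in either arm.

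The repeat rule adds a second dependence on the result. A sample showing hematuria can prompt a repeat, while no matching rule covers a low result, and the rule is not confined to Screening.

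Timing matters too. Section 3.6 leaves sponsor personnel unblinded, and Section 7 requires the SAP only before database lock. A contrast chosen later could be chosen with knowledge of allocation.

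**Working it through.** **1. The plan's own figure.** The protocol states no precision for hematuria. Its one precision figure is in Section 7.1: a 90% interval of width 0.80 for log UPCR, with log SD 0.597 and 9 and 18 patients. Check: 2 × 1.645 × 0.597 × √(1/9 + 1/18) = 2 × 1.645 × 0.597 × 0.408 = 0.802. This is reproduced. The study is therefore built on estimates with 90% intervals, which is the standard hematuria does not get.

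**2. Endpoint by endpoint (Section 7.2.5.2).**

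| Endpoint | Between-arm estimate stated |
|---|---|
| 24-hour urine protein | yes, as for the primary |
| Spot UPCR | yes, as for the primary |
| Partial remission | yes, difference with Wilson-based 90% CI |
| >50% reduction | yes, difference with Wilson-based 90% CI |
| Hematuria (dipstick) | none |

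**3. What selection on up to three tests does.** If single-test positivity is p and tests are independent (an assumption), the pass rate is 1 − (1 − p)³. For p = 0.3 this is 1 − 0.343 = 0.657; for p = 0.5 it is 1 − 0.125 = 0.875.

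**4. Which baseline, and how much it matters.** Section 6.3 requires a pre-dose urinalysis on Day 1, after a 14-week run-in. Section 7.2.8 takes the last observation on or before Day 1, but for safety. Section 7.2.4 speaks only of 24-hour UPCR. To size the choice, a latent hematuria level was simulated and cut into five dipstick grades. Patients entered at their first 2+ or higher on up to three Screening tests (placed 18, 17 and 16 weeks before Day 1), with no drug effect. Assumed, and not in the documents: between-patient share of variance 0.4 to 0.8; within-patient serial correlation per 4 weeks of 0, 0.5 or 0.8; single-test positivity 30% or 50%; entry by dipstick only.

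| Baseline used | Mean change to Week 32, grades |
|---|---|
| Qualifying Screening test | -0.32 to -1.30 |
| Day 1, correlation 0 | 0.00 (within ±0.01) |
| Day 1, correlation 0.5 | -0.01 to -0.05 |
| Day 1, correlation 0.8 | -0.08 to -0.30 |

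Day 1 removes most of the artifact. What is left has the same expectation in both randomized arms, so with no drug effect the expected arm difference is zero whichever baseline is used.

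**5. Is a contrast computable at this size?** Take illustrative counts of 12/20 v 3/10 patients improving and z = 1.645. The Wilson limits for one arm are [p + z²/2n ± z√(p(1−p)/n + z²/4n²)] / (1 + z²/n).

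- 12/20: 0.419 to 0.758.
- 3/10: 0.127 to 0.558.
- Difference: 0.60 − 0.30 = 0.30.
- Lower limit: 0.30 − √((0.600 − 0.419)² + (0.558 − 0.300)²) = 0.30 − 0.316 = -0.016.
- Upper limit: 0.30 + √((0.758 − 0.600)² + (0.300 − 0.127)²) = 0.30 + 0.234 = 0.534.

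That is 30 points, 90% CI about -2 to 53. With 9/18 v 3/9 the same method gives 17 points, -16 to 43. The contrast is estimable but imprecise.

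**The case against.** The best defense is that describing one secondary endpoint in a study of about 30 patients, sized on UPCR, is a legitimate choice. Section 7.2 calls its plans brief summaries, with more in the SAP, which is not at hand. A sentence promising descriptive statistics does not forbid a comparison, and a baseline or shift table is ordinary SAP content. This lowers the weight of the point but does not remove it. Section 7.2.5.2 does not leave the hematuria method open: it names one, and it is a weaker one than the same section gives the other four endpoints. Section 7.2.5.3 lets even exploratory efficacy variables receive inferential statistics as needed; the hematuria sentence has no such clause.

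Two stronger readings are tempting, and the documents do not support them.

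- A reader might infer that both arms will appear to improve with an inactive drug. That requires the qualifying Screening test to be the baseline. Sections 6.3 and 7.2.8 point instead to a fresh Day 1 sample. If each patient's chance of a 2+ result were constant and tests independent, expected change from Day 1 would be zero. Microscopy alone can also qualify a patient, so selection is not purely on dipstick.
- A reader might infer that ordinal grades will be averaged. Section 7.2 provides frequencies and percentages for ordinal variables, so this complaint is largely met.

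Nor is arm-specific bias shown for the repeat rule. Site staff and patients are blinded through Week 36, and Section 6.4.2 says only that a repeat may be needed, for menses or exercise.

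**Conclusion.** The point holds in a limited form. A stated secondary objective about drug effect has no planned estimate of that effect, although the same section already contains a suitable method. The absence of a named efficacy baseline for hematuria is a real ambiguity. Its cost ranges from near zero, if Day 1 is used, to an apparent fall of 0.32 to 1.30 grades with no drug effect, if the qualifying test is used. Those sizes rest on the assumed simulation ranges; the documents give no hematuria variability. The result-dependent repeat rule is a smaller weakness of the same kind, with no size that can be derived from the protocol.

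The protocol does not establish that hematuria will seem to improve without a drug effect, and that should not be claimed. The matter is modest in a small Phase 2 estimation study and does not touch the primary analysis, but it is worth correcting because the repair is nearly free.

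**What to change.** In Section 7.2.5.2:

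- Name the Day 1 pre-dose sample as the hematuria baseline.
- Keep the descriptive change and add a Day 1 to Week 32 shift table, both by arm.
- Add a between-arm estimate that uses baseline. One example is the difference in the percent of patients improving by at least one dipstick grade from Day 1 to Week 32, with the Wilson-based 90% interval already used for the two proteinuria responder endpoints.
- Use the percent below 2+ at Week 32 only as a supportive summary, among patients at 2+ or above on Day 1. Taken over all patients it ignores baseline and counts those already below 2+ as successes.

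In Section 6.4.2, base any repeat at post-baseline visits on menses or exercise recorded before the result is known.

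The cost is wording in two sections and one extra table, with no new samples or patients. The downsides are a wide interval at about 20 v 10 patients, and that a patient already negative on Day 1 cannot improve; the shift table will show how many there are in each arm.
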